3.4 ECD workshops for scriptwriters

We have run three ECD workshops with DMI scriptwriters in Burkina Faso to develop a team ethos around our shared objectives and values regarding ECD, to consider issues of equity, culture and tradition as they pertain to ECD concepts, and to build a shared language and common understanding of how ECD practice can be translated into radio for the SUNRISE project. Central topics have included reviewing the fundamental concepts underpinning ECD and the nurturing care framework, in-depth discussion of the more subtle and potentially challenging concepts to convey on radio, particularly responsive caregiving, and cultural barriers to acceptance of some ECD practices (praise, discipline, and individualist versus collectivist notions of childcare). These workshops will continue in parallel with the formative research so that this learning is incorporated in the team's thinking about content development for the radio campaign.

3.5 Message briefs

For each key behaviour in the curriculum, we will synthesize findings from the strands described above into a 1-page message brief. These briefs make the research more accessible to the script writing team and bridges the gap between research and creativity. Our team of scriptwriters will use these message briefs to write approx. 60 dramatic scripts and long format content, which will go through a validation process involving creative staff in both Burkina Faso and London. The best scripts are then produced and pretested in multiple languages using FGDs to test for clarity, popularity, and understanding. The final spots and long format content will then be selected and distributed for broadcast.

Post broadcast feedback will be obtained through periodic focus group discussions (FGDs) to find out whether people have heard and understood the campaign messages, their reaction to them and whether there are any remaining obstacles to behaviour change. Spots and long format content are then revised based on these findings.

4. SUNRISE Cluster Randomised Trial (CRT)

4.1 Trial clusters

The trial clusters are defined by the broadcast reach of local radio stations. Eligible clusters for the trial were identified as follows. First 23 potential clusters in areas of Burkina Faso where there is no security risk were identified by modelling the reach and signal strength of local radio stations based on tower location, antenna characteristics, and terrain features. A

[figure not shown]
media survey was then carried out to check the radio stations listened to in each of these clusters.

This resulted in 15 clusters which satisfy the following conditions: there are at most two dominant radio stations within the cluster; there is no discernible broadcast from stations in neighbouring clusters; they are not based in the large cities of Ouagadougou or Bobo-Dioulassou; and they are not subject to any security risk. The clusters and their radio station(s) are detailed in Table 2 and their locations are shown in Figure 2.

Table 2: Clusters with their Main Town & Local Radio Stations

Cluster	Town	Local Radio Station(s)
1	Banfora	Radio Munyu
2	Gaoua	Radio RTB2 Sud-Ouest
3	Dano	Radio Manivelle de Dano
4	Poura	Radio Poura
5	Boromo	Radio La Voix des Bales
6	Leo	Radio Tampani
7	Sapouy	Radio Loudon
8	Po	Radio Goulou
9	Zabre	Radio Paglayiri
10	Bittou	Radio Zekoula
11	Dedougou	Radio Salaki
12	Gourcy	Radio Savane FM Nord; Radio Unite, Gourcy
13	Koudougou	Radio Palabre; La Voix du Sanguier
14	Kaya	Kaya FM; Radio Manegda
15	Pouytenga	Radio Pognere

Figure 2: Location of clusters

4.2 Mapping evaluation areas & Mobilising communities

Trial participants will be recruited from an evaluation area within each cluster that is close to the radio station(s), has a high signal strength confirmed by a motorbike survey and likely to have a high listenership based on the media survey. The following will be excluded from the area: towns, villages within 5 Km of towns, villages already on the national electricity grid and villages with populations of 5000 or more as they are likely to be a priority for the national electrification programme. These exclusions have been chosen to maximise the local radio station(s) as the main communication channel, with minimal audiences lost to television. The boundaries of the evaluation area will be defined such that they cover populations of 10-15,000 after these exclusions.

All households will be mapped using GPS coordinates, and household numbers allocated. This will be carried out by a team of 15 fieldworkers (FWs; 1/cluster), supported by 5 field supervisors. Before starting they will arrange meetings with the village elders, explain the purposes of the study and seek permission to proceed.

4.3 Baseline survey

4.3.1 Inclusion criteria

All mothers with a child/children aged less than 3 years will be eligible to be included in the baseline survey.

4.3.2 Exclusion criteria

Mothers who are visiting or are only temporary residents in the village ie. mothers who do not expect to be resident for the next 6 months.

4.3.3 Data collection

A baseline survey will be carried out before the start of the campaign. Fieldworkers will explain the study using information sheets in the relevant local languages and ask for consent to collect data from all eligible mothers with a child/children aged less than 3 years. Data will be collected on tablets and will comprise socio-demographic and socio-economic factors; parental education levels and literacy; and radio ownership and listening patterns. In addition, the FWs will administer the following to mothers of children aged 2 years:

- the short form of the Caregiver Reported Early Development Instruments (CREDI (34)) which is designed to serve as a population-level measure of ECD for children from birth to age three, and which has 20 questions primarily focused on milestones and behaviours that are easy for caregivers to understand, observe, and describe.
- The Family Care Indicators (FCI, (35)) survey developed by UNICEF to assess key caregiving/family home environment variables considered critical for early child development. This has been used very extensively, including in the global MICS surveys (36).

Data from the baseline will be used to:

1. Inform the content of the SUNRISE radio campaign through: Understanding gaps in responsive parenting, provision of early learning opportunities and overall ECD status; Provision of detailed radio listenership data including the stations families listen to, the duration and timing during the day when they listen to radio, and exposure to specific radio programs.
2. Provide a sampling frame for the surveillance system of 3-monthly household visits that will be used to recruit trial participants and conduct ECD assessments with GIS maps of households of households within the EAs. These maps will be used to develop detailed field visit schedules for field workers; create day and week work groups based on optimal workload distribution and geographical proximity of households to ensure that all eligible families are visited on schedule at regular intervals.
3. Carry out the restricted randomization (see section 4.4 below).

4.4 Randomisation of clusters

The SUNRISE campaign will be broadcast by the local radio stations in eight of the clusters chosen at random to be in the intervention group; the other 7 clusters will be in the control group and their radio stations will continue to broadcast as normal. This will be carried out using restricted randomization to ensure that the intervention and control clusters are balanced at baseline with respect to radio exposure and predictors of ECD outcomes as follows:

- Mean CREDI z-score; difference between intervention and control groups to be a maximum of 0.1.
- Mean % key FCI behaviours followed by mothers; difference between intervention and control groups to be a maximum of 10%.
- % mothers listening to the radio in the last week; difference between intervention and control groups to be a maximum of 10%.
- % mothers who are literate; difference between intervention and control groups to be a maximum of 10%.

The restricted randomization will be carried out by the independent trial statistician using the cvcrand command¹ in Stata. This performs covariate-constrained randomisation which is suitable for cluster randomised trials with a small number of clusters. The 20% most balanced allocation schemes using the four variables described above will be generated. This subset will then be checked to ensure that it is not a biased selection by checking for anomalies in the frequencies of co-allocations of pairs of clusters. If bias happens, the restricted randomisation will be repeated using the CREDI criteria plus 2 of the other three. One allocation scheme will then be selected at random from the final restricted randomisation results and shared with the campaign team but not with the trial evaluation team.

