4.11 Statistical Methods

Findings will be reported according to the CONSORT guidelines for cluster randomized trials. Analyses will be intention to treat and include all data from trial children and their families, regardless of their exposure to the radio campaign. Random-effects linear regression models using individual-level data will be used to adjust for the clustered design and any imbalances between intervention and control arms. Effect sizes will be presented as standardized mean differences with 95% confidence intervals (CI). The data analysis plan will be published prior to the end of recruitment.

Analyses will initially be carried out blind with clusters randomly allocated randomly to groups X & Y. Results will be presented to the TSC /DMEC and all data procedures and statistical methods agreed. This is in order to ensure that any decisions made concerning methods, choice of indicators, outliers etc cannot be influenced by the trial results. Partially unblinded analyses will then be presented with the two trial groups labelled by letters rather than as intervention and control. The findings will be discussed, and the interpretation of any differences agreed, ignorant to the knowledge of which group is intervention and which control. The code will then be broken. Interpretation of findings cannot be changed at this stage.

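### Does section 4.4 need a rule tying its four maximum baseline differences to the best-20% selection step?

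*Protocol*

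**What the plan says.** Section 4.4 of the protocol allocates 15 clusters, with "eight of the clusters chosen at random to be in the intervention group; the other 7 clusters will be in the control group". It gives the purpose first: "This will be carried out using restricted randomization to ensure that the intervention and control clusters are balanced at baseline". Four bullets follow, each naming a variable and a ceiling. The first reads "Mean CREDI z-score; difference between intervention and control groups to be a maximum of 0.1". The other three set 10% for key FCI behaviours, for mothers who listened to the radio in the last week, and for literate mothers.

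The procedure comes next. The independent trial statistician runs cvcrand in Stata, and "The 20% most balanced allocation schemes using the four variables described above will be generated". That subset is checked for odd frequencies of pairs of clusters landing in the same arm. If the check fails, there is a fallback: "If bias happens, the restricted randomisation will be repeated using the CREDI criteria plus 2 of the other three". Finally, "One allocation scheme will then be selected at random from the final restricted randomisation results".

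Section 4.11 adds that the regression models will "adjust for the clustered design and any imbalances between intervention and control arms".

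**The concern.** The bullets are absolute limits and the selection step is a ranking. The ranking step refers to the variables, not to their ceilings, and the only later check concerns pairs of clusters, not balance. Taken literally, the steps never compare a scheme with a ceiling. If the clusters differ widely at baseline, even the best fifth of schemes can include some that break one.

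The fallback seems to add a second gap. One variable leaves the restriction, and the text does not say outright that its ceiling goes with it.

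At stake would be weaker baseline balance than the section promises, in a trial with few clusters that counts restriction among its protections against bias (section 4.13). An auditor also could not say for certain whether an allocation with, for example, a 12-point literacy difference had followed the protocol.

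**Working it through.** **1. Number of schemes.** The design has 15 clusters split 8:7 (sections 4.1 and 4.4). C(15,8) = 6,435 schemes, and 20% of these is 1,287. The section states no figure for the share of schemes meeting the ceilings, so there is none to reproduce.

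**2. How tight the ceilings are.** For a cluster-level variable with between-cluster SD *s*, the arm difference under unrestricted allocation has SD *s* × √(1/8 + 1/7) = 0.518 *s*. The protocol gives no *s* for any of the four variables, so these values are assumptions. For CREDI, 0.1 and 0.2 are the square roots of the intra-class correlations 0.01 and 0.04 in section 4.10, which are not stated for baseline CREDI. For the percentages, 10, 15 and 20 points are used.

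- CREDI *s* = 0.1 or percentage *s* = 10: SD of the difference 0.052 or 5.2 points. The ceiling lies 1.93 SDs out, and about 95% of all schemes meet it.
- CREDI *s* = 0.2 or percentage *s* = 20: SD of the difference 0.104 or 10.4 points. The ceiling lies 0.97 SDs out, and about 67% meet it.

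For four independent variables this gives roughly 0.946⁴ = 0.80 and 0.666⁴ = 0.20 of all schemes meeting every ceiling. Full enumeration on simulated cluster means gave 82% and 19%. With small spread the 20% cut is the stricter rule. With large spread the ceilings also bind.

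**3. Breaches if the ceilings were ignored.** All 6,435 schemes were scored, the best 1,287 kept, and those breaking at least one ceiling counted (400 simulated data sets per setting). The score form and correlation are assumed too.

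| Score, correlation | 0.1; 10 | 0.1; 15 | 0.1; 20 | 0.2; 10 | 0.2; 15 | 0.2; 20 |
|---|---|---|---|---|---|---|
| Squared, 0 | 0% | 3% | 19% | 6% | 9.5% | 25% |
| Squared, 0.4 | 0% | 1% | 12% | 4% | 5% | 16% |
| Absolute, 0 | 0.5% | 8% | 24% | 8.5% | 16% | 32% |
| Absolute, 0.4 | 0.1% | 4.5% | 17% | 6% | 10.5% | 24% |

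Columns give the CREDI SD and the percentage SD in points. A separate run with wider SDs (squared score, independent) had 62% of kept schemes compliant at 0.30 and 20 points, and 30% at 0.40 and 25 points, so breaches of 38% and 70%.

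**4. Size of a breach.** At CREDI SD 0.2 the median breaching difference is 0.11 (squared) or 0.12 (absolute) against 0.10. The largest in the kept set averages 0.13 or 0.18. At percentage SD 20 the median breach is 11 to 12 points against 10. Suppose, as a deliberately severe assumption, that a baseline CREDI difference passed one-for-one into the standardised outcome with no adjustment. The median excess of 0.01 to 0.02 would then be 4 to 8% of the 0.25 effect size in section 4.10. The largest excess, 0.03 or 0.08, would be 12 or 32%, but that is a single scheme among 1,287.

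**5. If the ceilings are applied.** Breaches are then zero by construction. The question becomes whether enough schemes remain. After the 20% cut (squared score, independent) the mean number left is 1,287 at (0.1; 10), 1,210 at (0.2; 10), 1,043 at (0.1; 20) and 961 at (0.2; 20), with a worst data set of 417. Each of these leaves a workable set.

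**6. The fallback.** Under three-variable scoring (squared, independent, CREDI SD 0.2), the dropped variable exceeds 10 points in 5, 20 and 33% of kept schemes at percentage SD 10, 15 and 20. Set beside "If bias happens, the restricted randomisation will be repeated using the CREDI criteria plus 2 of the other three", this is what the plan intends: three criteria are kept and one is released so that the pair check can pass. Enforcing all four would leave 1,191, 1,007 and 804 schemes, against 1,255, 1,250 and 1,199 with the three retained ceilings, and so partly undo the fallback.

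**The case for a change.** The strongest case for a change is that the protocol chose to fix the randomisation procedure itself, with numbers, and the procedure has to be executable before the campaign starts. The analysis plan is due only before the end of recruitment (section 4.11), after allocation, so it cannot close the gap. Three readings can be built from the text: ceilings as a filter, as a description of what the cut should achieve, or as the restriction itself. They yield different sets of schemes.

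Some of this stands. A linking sentence is missing, and no other section supplies one. The fallback also does not name which two of the three remaining variables are kept.

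The readings are not equally natural, though. The section states an aim to ensure balance, lists maxima as the way to do so, and then refers back to the CREDI entry as a criterion. A statistician who drew a scheme above a printed maximum would have to disregard the lines just above the procedure. Choosing two of the three variables uses baseline data only. Trial children are born at least three months after launch (section 4.6.1), so no outcome data exist that could steer the choice. The audit worry is also limited: the baseline survey collects all four variables (section 4.3.3), so the achieved differences can be set against the ceilings at any time.

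A hard-wired filter has its own price. At (0.2; 20) it widens the average range of pairwise co-allocation from 0.26–0.66 to 0.24–0.68, against (28 + 21)/105 = 0.47 unrestricted. That is a small step towards the anomaly the pair check looks for.

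**Conclusion.** This is a gap in wording that a competent statistician fills sensibly, and the plan need not change. On the natural reading the maxima are acceptance limits, no drawn scheme exceeds one, and the fallback releases exactly one of them.

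On the least favourable reading the consequence is somewhat weaker balance. Breaches would occur in 0 to 32% of kept schemes on the main grid and up to 70% at the widest spread tried, mostly by small margins where their size was examined. All of those frequencies rest on between-cluster SDs, score forms and correlations that the protocol does not give. They show that a rank cut differs from an absolute limit, not that this trial will be unbalanced.

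On either reading the scheme is drawn at random from a set fixed by baseline data, and the planned regression can adjust for remaining imbalance. No effect on type I error, power or the trial's conclusion has been shown.

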4.5 Interventions

4.5.1 SUNRISE clusters

All caregivers and the children they care for will have the potential to benefit from the SUNRISE radio campaign broadcast on their local radio stations which will be promoting responsive caregiving and providing opportunities for early learning to support child development during the first three years of life. They may also benefit from any other programmes broadcast concerning maternal, newborn and child health and wellbeing as well as from the routine maternal and child health services currently available.

4.5.2 Control clusters

Radio stations in the control clusters will continue to broadcast as normal. Caregivers and the children they care for may benefit from any programmes broadcast concerning maternal, newborn and child health and wellbeing as well as from the routine maternal and child health services currently available.

4.6 Trial Participants

The first 125 eligible children born in each cluster after the campaign has been running for three months will be enrolled together with their families. They will be identified through 3-monthly surveillance visits to all compounds identified at baseline; it is expected that recruitment will be achieved within a 6-month period. They will form the **trial cohort** and be followed 3-monthly until the end of the radio campaign. Its impact on ECD nurturing care behaviours and ECD outcomes in the first 3 years of life will be evaluated.

Everyone with access to a radio in the intervention clusters can potentially hear the campaign messages and long programmes. The selection of mothers for the trial cohort to evaluate the impact of the campaign has been specifically chosen to ensure their maximum potential exposure to the SUNRISE radio campaign in the intervention clusters as this will be broadcast during their last trimester of pregnancy until the final ECD outcome assessment of their children.

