More specifically, SUNRISE aims to develop and evaluate a radio campaign to promote nurturing care behaviours in the first 3 years of life, particularly responsive parenting and providing opportunities for early learning. These are the two components of the nurturing care roadmap which promote physical, social, emotional and cognitive development by ensuring: 1) Children have secure emotional attachments with caregivers; 2) Caregivers are sensitive and responsive to the child’s cues; 3) Caregiver-child interactions are enjoyable and stimulating; 4) Communication is bi-directional; 5) Communication is language rich and 6) There are opportunities for play and early learning (10).

The specific objectives are:

1. To design and implement a nurturing care radio campaign in Burkina Faso.
2. To evaluate the impact on ECD outcomes using a cluster randomised trial (CRT) design.
3. To carry out a detailed process evaluation.
4. To cost the delivery of the campaign and estimate the cost-effectiveness when delivered at scale, compared to other approaches.
5. To create ECD communications capacity in Burkina Faso, enabling a national scale-up.
6. To develop a roadmap to advise governments in low and middle-income countries on media campaigns for ECD.

2. Overview of SUNRISE CRT

The SUNRISE campaign will comprise: 60-second radio ‘spots’ including scripted dramas and modelling of responsive parent-child interactions broadcast 10 times a day in 6 languages in weekly cycles; plus long format programs 2-3 times a week, incorporating longer dramas, real life testimonials and practical ‘how to’ advice, with space for listeners to call in, express opinions and ask questions. The campaign will run for 3 years with its impact on early child

development (ECD) evaluated using a cluster RCT design; the clusters will be defined by the broadcast reach of local radio stations.

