Fifteen clusters have been identified from across Burkina Faso which satisfy the following conditions: there are at most two dominant radio stations and no discernible broadcast from stations in neighbouring clusters; they are not based in the large cities of Ouagadougou or Bobo-Dioulassou; and they are not subject to any security risk. Eight will be randomised to broadcast the SUNRISE campaign and 7 to act as controls. One hundred and twenty-five babies from each cluster who are born after the campaign has been running for 3 months will be enrolled into the trial and have six-monthly ECD assessments conducted throughout the campaign. All trial procedures will be carried out in full compliance with Good Clinical Practice (GCP) guidelines.

3. The SUNRISE Radio Campaign

The SUNRISE campaign builds on the saturation+ approach successfully used in DMI's previous child survival campaign in Burkina Faso promoting family health behaviour and care seeking for sick children. This approach is based on:

1. Saturation: Broadcasting approximately 10 times per day
2. Science-informed content: Using a variety of evidence-based methods and behaviour change theories to inform campaign design
3. Stories: Using innovative creative techniques within both spots and interactive programming to maximise audience engagement

The SUNRISE campaign will follow DMI's established intervention approach & implementation schedule with:

1. 60-second radio spots, tailored to increase awareness, knowledge, motivation, skills and opportunity regarding the target behaviours. These spots are highly cost-effective as they are short, entertaining and can be repeated multiple times. Over 100 different spots will be produced. We will achieve population saturation of messaging within cluster sites by broadcasting these 60 second spots 10 times every day in each of 6 languages for a week. This weekly cycle will continue for three years. 60-second radio 'spots' broadcast in weekly cycles, 10 times a day, and in 6 languages (i.e. one or two spots plays intensely for a week and then replaced with new spots for the following week and so on). These will include scripted dramas and modelling of responsive parent-child interactions.

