4.6.1 Inclusion criteria

Live newborns with a birth date at least 3months following the launch of the SUNRISE radio campaign will be eligible to be enrolled into the trial.

¹ <https://journals.sagepub.com/doi/10.1177/1536867X1801800204>

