4.6.3 Informed consent

Participants will be approached and recruited from their homes by the trained fieldworkers, who will explain the study by reading an information sheet translated into the local languages of the 15 clusters in the trial. Where a local language does not have a commonly used written format, the information sheet will be written in French and translated orally into the local language by the interviewers, as practised during the training sessions. All translations will be validated using back translation plus pilot testing.

The information sheets include guidance on how information will be kept secure and confidential and the limits of confidentiality during home visits. Participants will be made aware that their decision to participate will not in any way impact their access to existing health services that they may already be accessing. After sharing this information, participants will have the opportunity to ask questions and their understanding will be verified before consent is requested.

If they are happy with the answers they have received and agree to take part, participants will complete a consent form, with their agreement to participate indicated by YES responses to all key aspects of the study followed by a signature on the consent forms, which the fieldworker will also need to sign. Consent will cover recruitment and the 11 follow-up 3-monthly visits. Separate, additional consent processes will be undertaken at the 18-20 month visit in order to obtain consent for video recording of parent-child interactions and at the 30-32 month (final) visit, when mothers will be asked to consent for their child to take part in a developmental assessment.

Signed consent forms will be kept by the mothers; the fieldworkers will take photos of these on their tablets.

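### Section 4.6 ends follow-up with the campaign at month 36, but the 30–32 month MDAT visits fall due up to about months 39–42

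*Protocol*

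**What the plan says.** On the length of the campaign, the Abstract and section 2 state: "The campaign will run for 3 years". Section 3 gives the same three years for the weekly broadcast cycle. No part of the protocol extends it.

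On the end of follow-up, section 4.6 says that cohort children will "be followed 3-monthly until the end of the radio campaign". Section 2 says that they will "have six-monthly ECD assessments conducted throughout the campaign".

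On who enters and when, section 4.6.1 admits "Live newborns with a birth date at least 3months following the launch of the SUNRISE radio campaign". Section 4.6 adds that "it is expected that recruitment will be achieved within a 6-month period".

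On the primary impact outcome, Table 3 and sections 4.7 and 4.8.1 place the MDAT at one visit only, visit 11, at age 30–32 months. Section 4.6.3 calls this the final visit and states: "Consent will cover recruitment and the 11 follow-up 3-monthly visits".

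On exposure, section 4.6 explains why these mothers were chosen: "this will be broadcast during their last trimester of pregnancy until the final ECD outcome assessment of their children". Section 4.8.1 likewise says that intervention families will have been exposed from late pregnancy onwards, for the whole of the child's life.

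**The concern.** The protocol fixes the end of follow-up in two ways: by calendar (the end of the campaign) and by age (the 30–32 month visit). The two coincide only for the earliest births. For later births, the calendar rule stops visits before the only MDAT assessment is due, and the age rule carries the assessment past the last broadcast.

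At stake is either the primary outcome of the later-born children, if staff apply the calendar rule, or the accuracy of the exposure statement, if they apply the age rule. The exposure statement is the stated reason for choosing this cohort, and readers will rely on it when they interpret the effect.

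**Working it through.** **Inputs (months counted from launch).** Campaign end: 3 × 12 = 36 (Abstract, sections 2 and 3). First eligible birth: month 3 (section 4.6.1). Recruitment: expected within 6 months, so about months 3–9 (section 4.6). MDAT age: 30–32 months (Table 3, sections 4.7 and 4.8.1). The bands in Table 3 run on without gaps (27–29, then 30–32), so in completed months the last band covers age 30 to just under 33.

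**The plan's own timetable.** A child born at month *b* is due for the MDAT between months *b* + 30 and *b* + 33.

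- Born at month 3: due in months 33–36. The plan's timetable works.
- Born at month 6: due in months 36–39. Only a visit at exactly 30 months falls within the campaign.
- Born at month 9: due from month 39 to months 41–42 (9 + 32 = 41; 9 + 33 = 42). The whole window is after the campaign.

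A child born after month 6 turns 30 months after month 36 (6 + 30 = 36). Children born between months 3 and 6 may also be seen after month 36, because households are visited on a three-monthly round and the visit can fall anywhere in the band.

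**Share assessed after month 36.** The protocol does not give the span of births or the exact age at visit, so both are assumptions here. Let births be even over *W* months from month 3 (*W* at least 3), and let age at the visit be even over *A* months from age 30 (*A* at most 3). Then

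share = 1 − (3 − *A*/2)/*W*.

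| Births even over | All seen at exactly 30 months (*A* = 0) | Ages 30–32 (*A* = 2) | Ages 30–33 (*A* = 3) |
|---|---|---|---|
| 3 months | 1 − 3/3 = 0% | 1 − 2/3 = 33% | 1 − 1.5/3 = 50% |
| 4 months | 1 − 3/4 = 25% | 1 − 2/4 = 50% | 1 − 1.5/4 = 62.5% |
| 6 months | 1 − 3/6 = 50% | 1 − 2/6 = 67% | 1 − 1.5/6 = 75% |

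A simulation gives the same values. Birth spans shorter than 3 months would lower the share further.

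**Which row applies.** If the 6 months must also contain a lag of up to 3 months between birth and the enrolment visit, births are complete by about month 6 (first row). If births themselves span the 6 months, the last row applies. The evaluation areas "cover populations of 10-15,000 after these exclusions", but no birth rate is given. For 125 enrolled births, a 3-month span means 125 × 12/3 = 500 a year, or 33–50 per 1,000 people. A 6-month span means 125 × 12/6 = 250 a year, or 17–25 per 1,000. The protocol's figures do not choose between them.

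**Gap in exposure if visits continue.** The latest assessment comes 39 − 36 = 3 months after the last broadcast if births end by month 6, and 42 − 36 = 6 months after it if births run to month 9.

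**The case against.** The strongest reply is that the age-based schedule plainly governs. Section 4.6.3 obtains consent for the full series of visits and names the 30–32 month visit as the final one. Table 3 and sections 4.7 and 4.8.1 agree, and section 4.10 counts on at least 100 assessed children per cluster. On this view, the phrase in section 4.6 is loose shorthand, written by someone who took the end of the campaign and the final assessment to coincide. This stands as a statement of what will probably happen. It does not make the sentence right, and it leaves the exposure statements untrue for later-born children.

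A second reply is that the schedule runs by age and not from the date of recruitment, and that recruitment is only expected within 6 months, so it may be faster. This also stands. A child born in month 4 and recruited in month 6.5 is due from month 34, so late recruitment alone does not put the MDAT past month 36. If births are complete within 3 months, every child reaches 30 months by month 36. Even then, none would be late only if every child were seen promptly at 30 months.

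A reader might infer that a large part of the primary outcome will be lost and that the trial will fall short of its planned power. The documents do not support that. It would happen only if staff set aside the consent text, Table 3 and section 4.8.1 and cancelled the primary outcome visit.

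**Conclusion.** The contradiction is real and needs correcting. Follow-up that stops at month 36 cannot contain the MDAT visit of any child born after month 6, and may miss it for some children born earlier. The visits fall due from month 33 to about month 39 if births are complete by month 6, and to about months 41–42 if births span the full 6 months.

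No single percentage can be read from the protocol. With births even over 6 months, at least 50% and up to about 75% of children are assessed after month 36. With births even over 3 months, the share runs from none to about half, depending on age at visit. These figures assume even births and that recruitment keeps to the expected 6 months.

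On the likelier reading, in which each child is followed to the 30–32 month visit, no data or power are lost. The comparison between arms is not biased either, since the calendar is the same in both. What remains is that the exposure statements in sections 4.6 and 4.8.1 are wrong by some months for the children assessed after broadcasting stops.

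**What to change.** 1. In section 4.6, replace the end point in "be followed 3-monthly until the end of the radio campaign" with *until each child's 30–32 month visit, whether or not the campaign is still on air*.
2. In section 2, align the statement that assessments run throughout the campaign with that end point.
3. State the calendar: MDAT visits start at month 33, and the last fall at up to about months 39–42 depending on the span of births, or later if recruitment overruns.
4. Reconcile the stated campaign length with the exposure statements in sections 4.6 and 4.8.1, so that readers know for how long the campaign was on air before each child's assessment.

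The cost is protocol wording. Data collection would run about 3 to 6 months past month 36, which the consented visit schedule already implies. No extra participants are needed.
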